IMPROVING INITIAL MANAGEMENT OF THE INJURED AT GHANAIAN DISTRICT AND REGIONAL HOSPITALS WITH A TRAUMA INTAKE FORM

- Protocol and Statistical Analysis Plan

NCT #: **NCT04547192**

Date: **December 3, 2019**

STUDY PROTOCOL

We propose a pragmatic randomized clinical trial to be carried out at 8 district and regional hospitals in Ghana. The intervention to be tested is the Trauma Intake Form (TIF) to be used in recording information about injured patients during their initial assessment and care and which is designed to serve as a memory prompt (built-in checklist) to decrease omission of critical steps in care and so to improve care and to improve record keeping. The unit of randomization will be hospitals and a stepped-wedge design will be used to select which hospitals will start use of the TIF at what time.

Overall Strategy and Methods.

Methods for specific aims 1 and 2.

Specific aim 1. *To determine the effectiveness of a model Trauma Intake Form (TIF) to function as a checklist for increasing the appropriate use of key performance indicators (KPIs) (e.g. airway maintenance, tests to exclude internal bleeding, examination of distal pulses, pulse oximeter placed) during care of the injured in emergency units in district and regional hospitals in Ghana, as assessed by independent observers.*

Specific aim 2. *To determine the percent of injured patients with adequate data on initial assessment before vs. after introduction of the TIF in emergency units in district and regional hospitals in Ghana.*

The effectiveness of the TIF will be assessed at the 8 study hospitals by measuring the use of KPIs during initial care of the injured before vs. after introduction of the TIF. Data on the KPIs will be obtained from *observations* by research assistants (RAs) of care provided by EHSPs and by *data from medical records*.

Data gathering. We will station 2 RAs in the emergency units of recruited hospitals to observe EHSP practices regarding initial care of the injured. To adequately capture EHSP practices across the entire work day, RAs will be stationed at each hospital's emergency unit in rotating 8-hour shifts. In the period before TIF introduction, RAs will use an observation form (derived from the TIF) to record the implementation (or lack thereof) of KPIs as they observe EHSPs assess and manage each injured patient. They will fill the form without interaction with EHSP or the patient. For any components of the assessment and management that they are unable to directly observe, they will obtain information from the patient records to complete the observation form before the patient leaves the emergency unit.

Additional data from medical records. They will complete the observation form with information from patient records (in the period before TIF introduction) and/or from the EHSP-filled TIF (during TIF use). Both before and after introduction of the TIF, RAs will review the medical records of all patients observed for additional details (as above) and for additional safety-related data, including occurrence of complications (e.g. infections) or death.

Methods for introducing the TIF. We will employ a stepped-wedge design in sequentially introducing the TIF to the 8 selected hospitals. We will consider two nearby hospitals as a group, thereby getting four groups of hospitals. First, following 14 weeks of initial observation of EHSP practices at all 8 selected hospitals, we will conduct a training workshop for EHSPs of the first randomly-selected group of hospitals on use of the TIF. Following the workshop, the EHSPs will be encouraged to begin use of the TIF at their hospitals. After another 14 weeks, we will conduct the training workshop for the next group of randomly selected hospitals, after which use of the TIF will begin at those hospitals. We will continue this sequential conduct of training workshops followed by use of TIF every 14 weeks until all 8 hospitals have been exhausted. The RAs will continue to observe EHSP practices for a further 14 weeks during which the TIF will be in use at all 8 hospitals. The total duration of observation of EHSP practices will be 70 weeks.

Data management and quality control. Data will be sent from the hospital sites to the Open Data Kit cloud repository, which employs end-to-end encryption and strict user credentials to ensure data security. A data manager will review new data from each site daily for the first week of data collection, then weekly during the first month and then monthly for the entire duration of the study. Additionally, the PI will engage the coordinator at each hospital by monthly phone calls for the first 9 months, and every 2 months for the next 9 months, to discuss study progress and address any concerns.

Sample size calculations

Statistical design and power.

Specific aim 1: We expect to enroll 25 patients per site per month and so, over the 17.5 months recruitment period at the 8 sites, a total of 3,500 patients. Assuming an alpha of 0.05 and the likely baseline values (Pre-

TIF) in Table 1, we have 80% power to detect (at a minimum) the post-TIF values indicated. We consider a range of coefficients of variation. Examples of several KPIs are shown for all injured patients and for a subset of seriously injured (referred or admitted ≥ 24 hours) patients, for whom additional KPIs apply. Based on pilot data, we anticipate 40% (n=1,400) of patients will be seriously injured.

Table 1. Sample size considerations

	Percent of patients		
	Pre-TIF	Post-TIF	Range
For all injured patients			
Blood pressure recorded on arrival	70*	77.6	77.4-77.6
Heart rate recorded on arrival	60*	68.2	67.9-68.2
Consciousness level checked on arrival	50*	58.5	58.1-58.6
For seriously injured patients (referred out or admitted ≥ 24 hours)			
Chest auscultated	85**	93.4	93.3-93.5
Internal bleeding ruled out by clinical exam, US, CT, DPL, or X-Ray	27**	39.0	38.0-39.5
Distal pulses in all 4 extremities examined	54**	67.1	66.7-67.3

Post-TIF values based on mid-range coefficient of variation (COV) of 0.25. Range is for COV of 0.15 to 0.40; *Baseline values from consensus of PI and investigators from multiple Ghanaian hospitals; **Baseline values from TCC study (3). US – Ultrasonogram, CT – Computer Tomography, DPL – Diagnostic Peritoneal Lavage

Specific Aim 2: The above patient numbers, alpha and power levels, and COV range apply. We are powered to detect an increase in the documentation of important clinical data (including *all* of: time of injury, mechanism of injury, respiratory rate, heart rate, blood pressure, consciousness level, temperature, and time of disposition) by at least 5% (10% to 15%).

Statistical Analyses for Specific Aims 1 and 2

We will perform descriptive statistics (e.g. percents, means) to describe characteristics of injured patients, including age, gender, mechanism of injury and initial diagnosis. For Spec Aim 1, we will create binary variables describing whether each of the KPIs of care (as specified by the TIF) were performed. Similarly, for Spec Aim 2, we will create a binary variable describing whether adequate data (*all* of the following: time of injury, mechanism of injury, respiratory rate, heart rate, blood pressure, consciousness level, temperature, and time of disposition) have been recorded for each patient. Differences in performance of KPIs or adequate data recorded will be estimated using generalized linear mixed models, adjusted for TIF introduction and time periods as fixed effects and hospitals and time periods as random effects. We will use STATA version 17 (College Station, TX) for all analyses. Data will be analyzed on an intention-to-treat basis.

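### Unseen Aim 1 KPI items are filled in from a source whose completeness is expected to change with the TIF, and the plan states no source code, coding rule or observed-only analysis

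*Combined protocol and SAP*

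**What the plan says.** Specific aim 1 describes the KPIs "as assessed by independent observers". Methods for specific aims 1 and 2 then names two sources: "Data on the KPIs will be obtained from *observations* by research assistants (RAs) of care provided by EHSPs and by *data from medical records". Use of records is therefore disclosed.

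Under Data gathering, for the period before the TIF, "RAs will use an observation form (derived from the TIF") to note whether each KPI is carried out. "For any components of the assessment and management that they are unable to directly observe, they will obtain information from the patient records". Additional data from medical records says that the form is completed with "information from patient records (in the period before TIF introduction) and/or from the EHSP-filled TIF (during TIF use"). It adds that, in both periods, "RAs will review the medical records of all patients observed for additional details".

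The opening of the Study Protocol says that the TIF is designed "to decrease omission of critical steps in care and so to improve care and to improve record keeping".

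Statistical Analyses for Specific Aims 1 and 2 turns each KPI into one binary variable, performed or not. It fits a mixed model with TIF introduction and time period as fixed effects and hospital and time period as random effects. Nothing there, or under Data management and quality control, mentions the source of an item, how to code an item neither seen nor documented, or a sensitivity analysis. The observation form itself is not reproduced.

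**The concern.** A fallback source is harmless to a before-versus-during comparison if it works equally well in both periods. Here the plan expects it not to. The TIF is a recording form, and Aim 2 is powered for a rise in complete documentation from 10% to 15%. A step that was done but not seen is more likely to be found in the paperwork once the TIF is in use, whether the TIF adds to the routine note or replaces it. Part of an Aim 2 gain could then be counted as an Aim 1 gain.

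Randomising the timing does not help, because the change in documentation arrives with the TIF. The model does not help either: it has no term for data source, so the artefact falls into the TIF coefficient.

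The point applies to KPIs defined by an action: consciousness checked, chest auscultated, pulses examined, internal bleeding ruled out. It is weaker for blood pressure and heart rate, which Table 1 words as recorded, so that documentation is part of the KPI. At stake is whether an Aim 1 result can be read as better care rather than better charting.

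**Working it through.** **1. The plan's own figures.** 25 x 17.5 x 8 = 3,500 patients, and 40% of these is 1,400. With 8 hospitals and 5 periods (70 weeks / 14), that is 3,500/40 = 87.5 patients per hospital-period, or 35 for the seriously injured. The Hussey-Hughes stepped-wedge variance for 4 groups of 2 hospitals is

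Var = 8s(s + 5t) / (40s + 120t),

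with s = pbar(1 - pbar)/n and t = (COV x baseline)^2. At COV 0.25, two-sided alpha 0.05 and 80% power, this gives post-TIF values of 77.6, 68.2, 58.5, 93.4, 39.0 and 67.1. All six match Table 1, so the sample size is not in question.

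**2. Inputs for the illustration.** True performance p is set to the Table 1 baseline. The documents do not give the following, so they are assumptions:
- unseen share u: 10% to 20%
- chance that a performed, unseen step is documented before the TIF: d0 = 0.5
- the same chance during the TIF: d1 = 0.7 to 0.9 (a gain of 20 to 40 points)
- no true change in care and no false entries.

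**3. Items neither seen nor documented coded not done.** Spurious gain = p x u x (d1 - d0), in percentage points. Measured baseline = p(1 - u(1 - d0)).

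| KPI | p | u 10%, gain 20 | u 10%, gain 40, or u 20%, gain 20 | u 20%, gain 40 | Measured baseline at u 20% | Detectable there | Chance of significance favouring TIF, last case |
|---|---|---|---|---|---|---|---|
| Internal bleeding | 27% | 0.5 | 1.1 | 2.2 | 24.3% | 11.6 | 0.08 |
| Consciousness | 50% | 1.0 | 2.0 | 4.0 | 45.0% | 8.5 | 0.26 |
| Distal pulses | 54% | 1.1 | 2.2 | 4.3 | 48.6% | 13.2 | 0.15 |
| Auscultation | 85% | 1.7 | 3.4 | 6.8 | 76.5% | 10.5 | 0.42 |

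The last two columns use the variance in step 1, and the nominal chance is 0.025. Auscultation in full: measured performance goes from 76.5% to 83.3%, so pbar = 0.799, s = 0.799 x 0.201/35 = 0.00459 and t = (0.25 x 0.765)^2 = 0.0366. SE is then 0.0388, 0.068/0.0388 = 1.75, and the normal probability at 1.75 - 1.96 is 0.42. As a share of the detectable difference, 6.8/10.5 = 65%.

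Staff are only asked to take the form up ("the EHSPs will be encouraged to begin use of the TIF at their hospitals"). If half of patients had a TIF, the gains would halve, to between 0.3 and 3.4 points.

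**4. Such items coded missing.** Let e be the share of unperformed, unseen steps that the TIF documents as not done (assumed 0 before the TIF). Then

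f(d, e) = [p(1 - u) + pud] / [(1 - u) + pud + (1 - p)ue], and bias = f(d1, e) - f(d0, 0).

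- Low case (u 10%, d 0.5 to 0.7): +0.3 to +0.5 points at e = 0, about zero at e = 0.2, and -0.3 to -0.6 at e = 0.4. Example, consciousness: f(0.5, 0) = 0.475/0.925 = 51.35%; f(0.7, 0) = 0.485/0.935 = 51.87% (+0.5); f(0.7, 0.4) = 0.485/0.955 = 50.79% (-0.6).
- Higher case (u 20%, d 0.5 to 0.9): +1.0 to +2.1 points at e = 0, and about -0.1 to -0.25 at e = 0.4.

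The unstated coding rule alone moves auscultation in the higher case from 6.8 to 1.0 points (e = 0).

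**5. Price of an observed-only analysis.** Scaling the SE by 1/sqrt(1 - u), power at the planned difference is the normal probability at 2.80 x sqrt(1 - u) - 1.96, which is 0.76 at u = 10% and 0.71 at u = 20%.

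**The case against.** The strongest reply is that few items will go unseen. Research assistants are stationed in the emergency unit on rotating shifts, and 25 x 12/365 = 0.82 patients per site per day is a light load. This is compatible with a small unseen share and stands as a reason for modest expectations. It does not establish the share, and the plan itself writes a procedure for unseen items. In the low case three of the four KPIs move by about 1 point or less, and internal bleeding and pulses stay well below their detectable differences even in the higher case. For internal bleeding a uniform documentation gain may be too high, since imaging can leave a result in the record without the TIF.

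Four stronger readings are tempting, and the documents do not support them.
- A reader might infer that using records breaks the promise of independent observation. The methods section names both sources, so it does not.
- A reader might infer that the bias must favour the TIF. That follows under not-done coding. Under missing coding the sign depends on whether the TIF also documents steps not done, which a checklist may well do.
- A reader might set 6.8 points for auscultation against the 8.4 in Table 1 and report 81%. That pairs a true rate of 85% with a difference calculated for a measured baseline of 85%. On the assumptions used, the measured baseline is 76.5% and the share is 65%. Taking 85% as already measured with the same losses (true rate 0.85/0.9 = 94.4%) would give 7.6 points and a chance of about 0.69. The documents do not say how the cited study measured its 85%, so this cannot carry the point.
- A reader might infer that nothing could be checked afterwards. Some of it could: records of all observed patients are reviewed in both periods, an item scored done with no record entry must have been seen, and Aim 2 measures documentation of consciousness level. These give partial bounds only.

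The form is not reproduced and may already carry a source field. The written plan does not say so.

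**Conclusion.** The concern holds as a gap in measurement and analysis, not as a fault in the randomisation or sample size. Followed as written, the plan can put a documentation change into the Aim 1 TIF effect for action-type KPIs. The size is unknown. On the stated assumptions it runs from negligible to about two thirds of the detectable difference for one KPI, auscultation, and only with 20% unseen, a 40-point documentation gain and not-done coding. The bias favours the TIF if items neither seen nor documented count as not done; otherwise it is smaller and its direction is open. False ticks on the TIF would add to it. Without an item-level source field the unseen share and the artefact can be only partly bounded later. It should be fixed because the remedy is cheap and the source of an item is hard to reconstruct once the data are collected. Confidence is medium, since the figures that decide the size are not in the documents.

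**What to change.** - On the observation form, record the source of each KPI item (directly observed, patient record, TIF, neither), if the form does not already do so.
- State one coding rule, the same in both periods, for items neither seen nor documented.
- Report the unseen share for each KPI before and during TIF use.
- Pre-specify an observed-only sensitivity analysis for Aim 1, with estimates and 95% confidence intervals shown beside the record-completed analysis, and discuss any divergence when interpreting improved care.

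The cost is one extra field per item and two or three sentences in the analysis section. The observed-only analysis has fewer evaluable items and the lower power shown in step 5 of the working. It may also be selective if being observed depends on severity, workload or TIF use. It should therefore stand as a sensitivity analysis and not replace the record-completed one.

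### Pairs of hospitals, not hospitals, are randomised, but neither the analysis model nor Table 1 allows for paired hospitals changing together over time

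*Combined protocol and SAP*

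**What the plan says.** The opening paragraph of the Study Protocol states: "The unit of randomization will be hospitals". Methods for introducing the TIF describes something different: "We will consider two nearby hospitals as a group, thereby getting four groups of hospitals". The draw is made among those groups: "we will conduct a training workshop for EHSPs of the first randomly-selected group of hospitals on use of the TIF". Both members of a pair therefore always start the TIF together. There are four steps and five 14-week periods ("The total duration of observation of EHSP practices will be 70 weeks").

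Statistical Analyses for Specific Aims 1 and 2 specifies a generalized linear mixed model "adjusted for TIF introduction and time periods as fixed effects and hospitals and time periods as random effects". It has no term for the pair or for pair by period, no clustering of standard errors by pair, and no small-sample reference distribution. The Table 1 footnote gives a single clustering parameter: "Post-TIF values based on mid-range coefficient of variation (COV) of 0.25", with a range of 0.15 to 0.40.

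**The concern.** Four units are randomised, with 4! = 24 possible orders. The analysis and the power calculation treat the eight hospitals as independent.

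The risk is specific. If two nearby hospitals share a change in some period (a referral pattern, staffing, local training), that change lines up with the step at which the TIF starts in that pair. A hospital-level model reads it as two independent pieces of evidence. The standard error of the TIF effect is then too small, type I error exceeds 5% and power is overstated. Similarity within a pair that is constant over time largely cancels from the comparison and is not the issue.

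The phrase about time periods as random effects does not close the gap on either reading. A calendar-period effect common to all hospitals adds nothing to the fixed period effects. A hospital-by-period effect still treats the two hospitals of a pair as independent.

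**Working it through.** **Inputs.** From Statistical design and power: 25 × 8 × 17.5 = 3,500 patients, so 3,500/40 = 87.5 per hospital-period. For the seriously injured, 1,400/40 = 35. COV is 0.25, alpha 0.05 (taken as two-sided), power 80%. The hospital SD is COV × baseline. The patient-level variance is p̄(1−p̄), with p̄ the mean of the pre and post values. All calculations use a linear model on hospital-period means, not the full binary GLMM.

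**Step 1: reproduce Table 1.** With eight independent hospitals, a hospital intercept, fixed periods and a normal reference, the detectable values are 77.57, 68.23, 58.52, 93.44, 39.02 and 67.06. The printed values are 77.6, 68.2, 58.5, 93.4, 39.0 and 67.1. Taking the four pairs as clusters gives 77.59, 68.26, 58.56, 93.46, 39.38 and 67.20, which misses five of six after rounding. Table 1 therefore carries no pairing.

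**Step 2: type I error due to pairing.** The documents give no pair-by-period variance, so a share of hospital variance is assumed to be period-specific. The formula is 2Φ(−1.96 × SE_model/SE_true).

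Worked example: blood pressure, fully shared pair-by-period SD of 2 points.
- Model with hospital-by-period effects: SE 2.93 against a true 3.15, so 2Φ(−1.96 × 2.93/3.15) = 6.8%.
- Model with hospital intercepts only: SE 2.70 against 3.15, giving 9.3%.

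Ranges over the six KPIs at COV 0.25, with hospital-by-period effects already in the model:

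| Period-specific share | None shared | Half shared | All shared |
|---|---|---|---|
| 1-2% | 5.0% | 5.0-6.4% | 5.1-7.9% |
| 10-20% | 5.0% | 5.3-9.4% | 5.7-13.7% |

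For scale, the blood pressure hospital SD is 0.25 × 70 = 17.5 points. A 1-2% share is an SD of 17.5√0.01 to 17.5√0.02 = 1.8-2.5 points. A 10-20% share is 5.5-7.8 points against a 7.6-point target, so that row is a stress case.

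With hospital intercepts only and full sharing, the figures are 5.1-12.7% (1-2%) and 6.4-47.4% (10-20%). Of these, 5.1-8.9% and 5.6-34.2% arise with no sharing at all, from the missing hospital-by-period term. That is a separate defect.

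A simulation for the consciousness KPI (600 runs per setting, full sharing) agrees. At pair-by-period SDs of 2, 3 and 5 points, type I error was 8%, 12% and 22% with hospital intercepts only, and 7%, 9% and 12% with hospital-by-period effects.

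**Step 3: power with no period-specific variance.** In a group-by-period cell analysis with fixed group and period effects, the double-centred sum of squares of the TIF indicator is 10 − 30/5 − 30/4 + 100/20 = 1.5, so SE = √[p̄(1−p̄)/(2n)/1.5]. For blood pressure, p̄ = 0.738 and n = 87.5 give SE = 0.0271. Residual df are 20 − 5 − 3 − 1 = 11 for four groups and 40 − 5 − 7 − 1 = 27 for eight hospitals.

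| KPI | Printed post | Power, plan's model, z | Cell, z | Cell, t 27 df | Cell, t 11 df | Detectable, 11 df |
|---|---|---|---|---|---|---|
| Blood pressure | 77.6 | 80.3% | 80.0% | 77.0% | 72.3% | 78.3 |
| Heart rate | 68.2 | 79.7% | 79.1% | 76.1% | 71.3% | 69.1 |
| Consciousness | 58.5 | 79.9% | 78.9% | 76.0% | 71.2% | 59.5 |
| Chest auscultation | 93.4 | 79.5% | 79.2% | 76.2% | 71.4% | 94.2 |
| Internal bleeding | 39.0 | 79.9% | 74.4% | 71.3% | 66.4% | 41.2 |
| Distal pulses | 67.1 | 80.2% | 78.4% | 75.4% | 70.6% | 68.6 |

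Under the plan's own model and z, four units instead of eight cost only 0.1-2.3 points of power (77.6-80.1%). Most of the fall below 80% comes from the small-sample reference and, for internal bleeding, the fixed effects. Moving from 27 to 11 df because pairs are randomised costs 4.7-4.9 points.

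**Step 4: do the alternatives hold their size?** The 20-cell analysis on 11 df gave type I error of 4.7-5.2% for all six KPIs with 0-20% shared variance (20,000 replicates per setting). A mixed model with hospital, hospital-by-period and group-by-period variances was simulated for the 50%, 70% and 85% KPIs (2,000 replicates per setting). It gave 4.5-8.8% with z and 2.2-5.8% with t on 11 df. Permutation over the 24 orders has a smallest p-value of 1/24 = 0.042 and power of only 53-59% at the Table 1 values.

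**The case against.** The strongest counter-argument is materiality. Nothing in the documents shows that paired hospitals change together; their being nearby is the only hint. With no sharing, pairing adds nothing to type I error, and time-constant pair similarity understates the standard error by only about 0.2-4%. At a 1-2% share, 7.9% is the worst KPI (chest auscultation, fully shared at 2%); internal bleeding stays at 5.1%, and with half sharing nothing exceeds 6.4%. The 13.7% figure needs shared shifts of SD 9.5 points (0.25 × 85 × √0.20) on a KPI with an 8.4-point target. Pairing alone barely moves Table 1. The mixed-model remedy was tested on linear means for three KPIs, and with t on 11 df it can be conservative.

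All of this stands as a limit on size. It does not remove the point. The two sections disagree on the randomised unit, and the size of the sharing is unknown, not known to be nil. Hospitals paired by proximity and trained in one workshop could plausibly share period-specific shifts. The plan names no reference distribution suited to four randomised groups. If the random time-period term already means hospital by period, the intercept-only figures fall away but the pairing excess remains.

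**Conclusion.** The concern holds and should be fixed. It is certain that four pairs are randomised, that the model has no pair-by-period term, that Table 1 assumes eight independent hospitals with a normal reference, and that no small-sample reference is stated. The inflation of type I error is conditional on shared period-specific change. It is modest at small shares (up to 7.9% at 1-2%) and serious only in the stress case (up to 13.7% at 10-20%, COV 0.25). Over the plan's COV range of 0.15-0.40, full sharing at 10-20% gives 5.3-15.1%. These figures rest on assumed variance shares and a linear approximation. They exclude the missing hospital-by-period term, which matters separately if the model has hospital intercepts only.

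**What to change.** 1. Correct the opening paragraph of the Study Protocol to name the pair of hospitals as the randomised unit.
2. Add hospital-by-period and group-by-period random effects to the model, or analyse the 20 group-period summaries with fixed group and period effects.
3. State a small-sample reference that reflects four groups. The 20-cell analysis with t on 11 df held its size in every setting tried. For the mixed model, z should not be used. Permutation over the 24 orders can serve as a check but is too weak to be the main test.
4. Restate Table 1 for the chosen analysis over a stated range of pair-by-period variance, for example 0, 1, 2, 5 and 10% of hospital variance.

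The cost is wording, two variance terms or a summary analysis, and a named reference; no new data. The price in sensitivity should be stated openly. With 11 df and no period-specific variance, detectable values become about 78.3, 69.1, 59.5, 94.2, 41.2 and 68.6. That is 0.7-2.2 points worse than printed, of which 0.4-0.8 points is due to 11 instead of 27 df. With 1-2% pair-by-period variance, power at the printed values under the same analysis falls to about 50-68%, from 66.4-72.3% without it.

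### Aim 1 names no primary endpoint, success rule or multiplicity method across its separately analysed KPIs, so the error rate of an effectiveness claim for the TIF is not controlled

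*Combined protocol and SAP*

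**What the plan says.** Specific aim 1 is to determine how effective the TIF is as a checklist that increases use of KPIs. Four KPIs are named there, as examples.

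The sample size section is written KPI by KPI. It begins "Assuming an alpha of 0.05 and the likely baseline values" and states that "we have 80% power to detect (at a minimum) the post-TIF values indicated". The rows are illustrative: "Examples of several KPIs are shown for all injured patients and for a subset of seriously injured" patients. Table 1 has six rows, three for all injured patients and three for the seriously injured.

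Under Statistical Analyses for Specific Aims 1 and 2, a binary variable is formed for each KPI that the TIF specifies. Then: "Differences in performance of KPIs or adequate data recorded will be estimated using generalized linear mixed models". That section gives no significance level, order of testing or adjustment, and does not say what pattern of results would count as effectiveness. The KPIs are not listed in full or counted anywhere in the document. Aim 2, by contrast, has one defined all-or-none variable per patient, but it concerns recording of data.

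**The concern.** The aim puts one overall question, and the plan supplies many answers to it without saying which one counts. A 0.05 level used for each KPI limits the error for that KPI. It does not limit the error of a statement about the TIF as a whole if that statement may rest on whichever KPIs improve. The six rows of Table 1 are only examples, and two of the four KPIs named in the aim (airway maintenance and pulse oximetry) are not among them, so Table 1 does not fix the set of tests either.

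At stake is how far a positive headline from Aim 1 can be trusted. The stated purpose of the form is to reduce omitted steps, yet no measure of omission per patient is defined, although the data for one are collected.

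**Working it through.** **Step 1: inputs from the documents.**
- Level and power: "Assuming an alpha of 0.05"; 80% power. Sidedness is not stated.
- Patients: "over the 17.5 months recruitment period at the 8 sites, a total of 3,500 patients" (25 × 8 × 17.5 = 3,500).
- Subset: "we anticipate 40% (n=1,400) of patients will be seriously injured".
- Design: 8 hospitals in 4 groups of 2; 70 weeks in steps of 14 weeks, so 5 periods and 40 hospital-periods. Patients per hospital-period: 3,500/40 = 87.5 overall and 1,400/40 = 35 in the subset.
- Variation between hospitals: "Post-TIF values based on mid-range coefficient of variation (COV) of 0.25. Range is for COV of 0.15 to 0.40".

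**Step 2: does Table 1 use an unadjusted 0.05 in each row?** The Hussey–Hughes stepped-wedge variance is

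Var = I·σ²(σ² + Tτ²) / [(IU − W)σ² + (U² + ITU − TW − IV)τ²]

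with I = 8 and T = 5. X is 1 for a hospital-period on the TIF and 0 otherwise:
- U, the sum of X: 2 × (4 + 3 + 2 + 1) = 20.
- W, the sum of squared period totals: 0 + 4 + 16 + 36 + 64 = 120.
- V, the sum of squared hospital totals: 2 × (16 + 9 + 4 + 1) = 60.
- IU − W = 160 − 120 = 40.
- U² + ITU − TW − IV = 400 + 800 − 600 − 480 = 120.

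Here σ² = p̄(1 − p̄)/n, with p̄ the mean of the pre- and post-TIF proportions and n the patients per hospital-period, and τ = COV × baseline.

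Blood pressure row, 70% to 77.6%:
- p̄ = 0.738; σ² = 0.738 × 0.262/87.5 = 0.00221.
- τ² = (0.25 × 0.70)² = 0.030625.
- SE = 0.0270; 0.076/SE = 2.814.
- Power at two-sided 0.05 = Φ(2.814 − 1.960) = 80.3%.
- At one-sided 0.05 it would be Φ(2.814 − 1.645) = 87.9%, so two-sided is the reading that fits.

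All six rows at COV 0.25:

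| KPI | Post-TIF value in Table 1 | Recomputed | Power at Table 1 value, level 0.05 | Same, level 0.05/6 | Detectable at level 0.05/6 |
|---|---|---|---|---|---|
| Blood pressure | 77.6 | 77.57 | 80.3% | 57.0% | 79.3 |
| Heart rate | 68.2 | 68.23 | 79.7% | 56.1% | 70.2 |
| Consciousness level | 58.5 | 58.52 | 79.9% | 56.3% | 60.6 |
| Chest auscultated | 93.4 | 93.44 | 79.5% | 55.8% | 95.1 |
| Internal bleeding ruled out | 39.0 | 39.02 | 79.9% | 56.3% | 42.1 |
| Distal pulses | 67.1 | 67.06 | 80.2% | 56.8% | 70.1 |

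Every row reproduces, so each was sized with the full two-sided 0.05. The last two columns give the price of a strict split over six tests (0.05/6 = 0.0083, critical value 2.638).

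**Step 3: chance of a false favourable result.** A false claim that the TIF works needs a result in its favour, so the rate for each KPI is 0.025. For k independent tests the chance of at least one is 1 − 0.975^k; for six, 1 − 0.975⁶ = 14.1%. Correlated cases come from 200,000 simulated sets of equally correlated normal statistics, counting any value above 1.96.

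| KPIs | Independent | Correlation 0.3 | 0.5 | 0.7 |
|---|---|---|---|---|
| 6 (Table 1) | 14.1% | 12.3% | 10.4% | 8.3% |
| 10 (assumed) | 22.4% | 17.7% | 14.5% | 10.7% |
| 20 (assumed) | 39.7% | 28.0% | 21.0% | 14.4% |

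The totals of 10 and 20 and all the correlations are assumptions. The documents give neither.

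**The case against.** Four points can be made for the plan.

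- **The analysis section speaks of estimating, not testing.** This is correct: 0.05 appears only in the power statement. A reader might infer that the plan tests every KPI at 0.05 and lets any single success count as effectiveness. The document says neither. The 0.05 per KPI is an inference, well supported by Step 2, and on what counts as effective the plan is silent. The silence is the defect, because the aim is to determine effectiveness and the study is sized for tests. If estimation alone is meant, the plan should say so.
- **The error rate can be overstated.** A reader might quote 1 − 0.95⁶ = 26% for six independent KPIs. That figure also counts KPIs that appear to worsen, which nobody would report as evidence for the form. The relevant figure is 14% or less for six KPIs.
- **The KPIs are bounded and matter individually.** The set is fixed by the form, which is not part of these documents, so it is not open-ended. The aim speaks of KPIs in the plural, and a clinician may want each one reported. Both points stand. They argue for keeping every KPI as a reported result, but they do not supply a rule for the overall conclusion.
- **Aim 2 already has a single endpoint.** It does, but for documentation, so it cannot carry the Aim 1 claim.

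A score also has weaknesses of its own: it treats all steps alike and can hide a critical step that did not change.

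**Conclusion.** The concern holds in this form: Aim 1 has no primary endpoint, success rule or multiplicity method, while each Table 1 example is sized at an unadjusted two-sided 0.05. With six KPIs and no TIF effect, the chance of at least one nominally significant result in favour of the TIF is 10–14% for correlations from 0.5 down to 0, about four to six times the nominal 2.5%. At correlation 0.7 it is still 8%. These figures assume equally correlated normal test statistics and a reader who accepts any one favourable KPI as evidence, which the plan does not say but does not exclude. The true figure depends on the number of KPIs on the form. The plan should be changed before analysis. The sample size does not become wrong: each Table 1 row stands as a single-KPI statement.

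**What to change.** Before analysis, name one primary endpoint for Aim 1 and test it once at two-sided 0.05. One suitable choice is each patient's proportion of applicable KPIs performed. It should include the additional KPIs for seriously injured patients, because Table 1 lists internal bleeding and distal pulses, both named in the aim, only for that subset. Keep the TIF, period and hospital terms of the planned mixed model, with an outcome distribution suited to a proportion. A single named primary KPI would also cure the defect and would keep its Table 1 power if taken from there.

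Report the individual KPIs as secondary estimates with confidence intervals and no separate claim of effectiveness, or Holm-adjust them if formal claims are wanted. List the KPIs and their number. Label Table 1 as unadjusted single-KPI detectable differences.

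**Cost.** SAP wording and one derived variable; no new data. Three drawbacks should be stated:
- The documents give no baseline or SD for a score, so its power cannot be computed from them. The pilot data that the sample size section mentions may help.
- The score weights all steps equally.
- Strict adjustment over six KPIs (0.0083 each, also Holm's first step) lowers power at the Table 1 values from 80% to about 56–57%. Reporting estimates only avoids this.
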